5.2.4 Electrocardiogram

5.2.4.1 12-lead resting ECG

Recording

Twelve-lead resting ECGs (I, II, III, aVR, aVL, aVF, V1 - V6) will be recorded using a computerised electrocardiograph at the time points given in the [Flow Chart](#). Electrode placement will be performed according to the method of Wilson, Goldberger and Einthoven modified by Mason and Likar (hips and shoulders instead of ankles and wrists). Precise electrode placement will be marked with an indelible mark on the skin to allow reproducible placement throughout the study.

To achieve a stable heart rate at rest and to assure high quality recordings, the site personnel will be instructed to assure a relaxed and quiet environment, so that all subjects are at complete rest.

All ECGs will be recorded for a 10 sec duration after subjects have rested for at least 5 min in a supine position. ECG recording will always precede all other study procedures scheduled for the same time (except for blood drawing from an intravenous cannula that is already in place) to avoid compromising ECG quality.

ECGs will be recorded as single ECGs or as triplicate ECGs (i.e. three single ECGs recorded within 180 sec) as indicated in the [Flow Chart](#).

ECGs may be repeated for quality reasons for instance due to alternating current artefacts, muscle movements, or electrode dislocation. For repetition within triplicate ECGs the time window of 180 sec applies as well. The repeat ECGs are assigned to the respective scheduled time point.

Additional (unscheduled) ECGs may be recorded for safety reasons. These ECGs are assigned to the prior scheduled time point in the sponsor's database.

Storing

All ECGs will be stored electronically in the System provided by a designated central ECG lab.

Data transfer

For time points specified in the [Flow Chart](#), ECGs will be transferred electronically to the central ECG lab for evaluation.

In case of repeat ECGs due to quality reasons, only the repeated ECG recordings will be transferred to the central ECG lab, whereas the initially recorded ECGs will be discarded. Unscheduled ECGs (for safety reasons) will be transferred to the central ECG lab but will not be included into the statistical analysis of interval lengths.

Data transfer from the central ECG lab to the sponsor is described in the ECG data transfer agreement (see TMF).

Evaluation

a) Central ECG lab

Central ECG lab evaluation will be performed for all time points with triplicate ECGs. For some time points, as indicated in the [Flow Chart](#), three triplicate ECGs are recorded (i.e. on days 1 and 19 in Part I and on day 1 in Part II). Always, only the first single ECG per triplicate will be evaluated. This will include the determination of cardiac QRS-axis, as assessed by the ECG machine's algorithm, as well as the intervals RR, PR, QRS and QT measured semi-automatically.

The remaining second and third ECGs of the triplicate ECGs will be stored for additional analysis if required, e.g., by authorities at a later time point.

Heart rate (HR) and the QT interval corrected for HR (QTc e.g. QTcF and QTcB) will be determined by the sponsor (see trial statistical analysis plan (TSAP) for details).

All semi-automatic interval measurements in one subject will be performed on the same lead. The intervals will be measured from four cardiac cycles (beats) in lead II. If lead II shows a flat T wave or is not measurable for any reason, lead V5 will be used, or if that lead is not measurable, then lead I will be used. The lead actually used will be reported in the CTR.

For automatic interval measurements no lead will be provided. After quality control, the fiducial point markings will be reviewed by the cardiologist assigned to the study.

For blinding arrangements see [Section 4.1.5](#). No more than two blinded readers will evaluate all ECGs of the study. ECGs from a particular subject should be evaluated by a single reader. For quality assurance and control of the measurements, all ECG of a subject will be subsequently reviewed by the ECG technician supervisor or his/her designee to assess the overall variance of the measured intervals and, to detect accidental switching of leads and/or false subject assignments of the ECGs. After quality control, the fiducial point markings will be reviewed by the cardiologists assigned to the study.

Evaluation of ECGs will comply with the ICH E14 guidance document and supplements [[R07-4722](#), [R16-0366](#)] as well as the FDA requirements for annotated digital ECGs [[R09-4830](#)].

b) Trial site

All local ECGs will be evaluated by the investigator or a designee.

For the inclusion or exclusion (see [Section 3.3](#)) of a subject and for the assessment of cardiac safety during the study, the QT and QTcF values generated by the computerised ECG system or their manual corrections by the investigators will be used.

In doubtful cases, ECGs may be sent upfront (i.e. prior to the regular data transfer) for cardiologic assessment by the central lab. In this case, these centrally measured results would overrule any other results obtained.

Proprietary confidential information © 2021 Boehringer Ingelheim International GmbH or one or more of its affiliated companies

Abnormal findings, irrespective of whether they originate from central or local evaluation, will be reported as AEs (during the trial) or baseline conditions (at screening) if judged clinically relevant by the investigator.

Any ECG abnormalities will be monitored carefully and, if necessary, the subject will be removed from the trial and will receive the appropriate medical treatment.

5.2.5 Assessment of adverse events

5.2.5.1 Definitions of adverse events

5.2.5.1.1 Adverse event

An adverse event (AE) is defined as any untoward medical occurrence in a patient or clinical investigation subject administered a medicinal product and which does not necessarily have to have a causal relationship with this treatment.

An AE can therefore be any unfavourable and unintended sign (including an abnormal laboratory finding), symptom, or disease temporally associated with the use of a medicinal product, whether or not considered related to the medicinal product.

The following should also be recorded as an AE in the CRF and BI SAE form (if applicable):

- Worsening of the underlying disease or of other pre-existing conditions
- Changes in vital signs, ECG, physical examination, and laboratory test results, if they are judged clinically relevant by the investigator

If such abnormalities already pre-exist prior to trial inclusion, they will be considered as baseline conditions and should be collected in the eCRF only.

5.2.5.1.2 Serious adverse event

A serious adverse event (SAE) is defined as any AE which fulfils at least one of the following criteria:

- Results in death
- Is life-threatening, which refers to an event in which the patient was at risk of death at the time of the event; it does not refer to an event that hypothetically might have caused death if more severe,
- Requires inpatient hospitalisation
- Requires prolongation of existing hospitalisation
- Results in persistent or significant disability or incapacity
- Is a congenital anomaly/birth defect
- Is deemed serious for any other reason if it is an important medical event when based upon appropriate medical judgment which may jeopardise the patient and may require medical or surgical intervention to prevent one of the other outcomes listed in the above definitions. Examples of such events are intensive treatment in an emergency room or at home for allergic bronchospasm, blood dyscrasias or

Proprietary confidential information © 2021 Boehringer Ingelheim International GmbH or one or more of its affiliated companies

convulsions that do not result in hospitalisation or development of dependency or abuse

An AE that possibly leads to disability will be ‘deemed serious for any other reason’ and reported as an SAE.

5.2.5.1.3 AEs considered ‘Always Serious’

Cancers of new histology and exacerbations of existing cancer must be classified as a serious event regardless of the time since discontinuation of the trial medication and must be reported as described in [5.2.5.2](#), subsections ‘AE Collection’ and ‘**AE reporting to sponsor and timelines**’.

In accordance with the European Medicines Agency initiative on Important Medical Events, Boehringer Ingelheim has set up a list of further AEs, which, by their nature, can always be considered to be ‘serious’ even though they may not have met the criteria of an SAE as defined above.

The latest list of ‘Always Serious AEs’ can be found in the electronic data capture (eDC) system, an electronic data capture system which allows the entry of trial data at the trial site.. These events should always be reported as SAEs as described above.

5.2.5.1.4 Adverse events of special interest

The term adverse events of special interest (AESI) relates to any specific AE that has been identified at the project level as being of particular concern for prospective safety monitoring and safety assessment within this trial, e.g. the potential for AEs based on knowledge from other compounds in the same class. AESIs need to be reported to the sponsor’s Pharmacovigilance Department within the same timeframe that applies to SAEs, please see section [5.2.5.2.2](#).

The following are considered as AESIs:

- Hepatic injury
A hepatic injury is defined by the following alterations of hepatic laboratory parameters:
 - o An elevation of AST (aspartate transaminase) and/or ALT (alanine transaminase) ≥ 3 -fold ULN combined with an elevation of total bilirubin ≥ 2 -fold ULN measured in the same blood sample, or
 - o Aminotransferase (ALT, and/or AST) elevations ≥ 10 fold ULN

These lab findings constitute a hepatic injury alert and the subjects showing these lab abnormalities need to be followed up according to the ‘DILI checklist’ provided in the ISF. In case of clinical symptoms of hepatic injury (icterus, unexplained encephalopathy, unexplained coagulopathy, right upper quadrant abdominal pain, etc.) without lab results (ALT, AST, total bilirubin) available, the Investigator should make sure that these parameters are analysed, if necessary in an unscheduled blood

Proprietary confidential information © 2021 Boehringer Ingelheim International GmbH or one or more of its affiliated companies

test. Should the results meet the criteria of hepatic injury alert, the procedures described in the DILI checklist should be followed.

5.2.5.1.5 Intensity (severity) of AEs

The intensity (severity) of the AE should be judged based on the following:

Mild: Awareness of sign(s) or symptom(s) that is/are easily tolerated

Moderate: Sufficient discomfort to cause interference with usual activity

Severe: Incapacitating or causing inability to work or to perform usual activities

5.2.5.1.6 Causal relationship of AEs

Medical judgment should be used to determine the relationship, considering all relevant factors, including pattern of reaction, temporal relationship, de-challenge or re-challenge, confounding factors such as concomitant medication, concomitant diseases and relevant history.

Arguments that may suggest that there is a reasonable possibility of a causal relationship could be:

- The event is consistent with the known pharmacology of the drug
- The event is known to be caused by or attributed to the drug class
- A plausible time to onset of the event relative to the time of drug exposure
- Evidence that the event is reproducible when the drug is re-introduced
- No medically sound alternative aetiologies that could explain the event (e.g. pre-existing or concomitant diseases, or co-medications)
- The event is typically drug-related and infrequent in the general population not exposed to drugs (e.g. Stevens-Johnson syndrome)
- An indication of dose-response (i.e. greater effect size if the dose is increased, smaller effect size if dose is reduced)

Arguments that may suggest that there is no reasonable possibility of a causal relationship could be:

- No plausible time to onset of the event relative to the time of drug exposure is evident (e.g. pre-treatment cases, diagnosis of cancer or chronic disease within days / weeks of drug administration; an allergic reaction weeks after discontinuation of the drug concerned)
- Continuation of the event despite the withdrawal of the medication, taking into account the pharmacological properties of the compound (e.g. after 5 half-lives). Of note, this criterion may not be applicable to events whose time course is prolonged despite removing the original trigger
- Additional arguments amongst those stated before, like alternative explanation (e.g. situations where other drugs or underlying diseases appear to provide a more likely explanation for the observed event than the drug concerned)

Proprietary confidential information © 2021 Boehringer Ingelheim International GmbH or one or more of its affiliated companies

- Disappearance of the event even though the trial drug treatment continues or remains unchanged

5.2.5.2 Adverse event collection and reporting

5.2.5.2.1 AE collection

Upon enrolment into a trial, the subject's baseline condition is assessed (for instance, by documentation of medical history/concomitant diagnoses), and relevant changes from baseline are noted subsequently.

Subjects will be required to report spontaneously any AEs as well as the time of onset, end time, and intensity of these events. In addition, each subject will be regularly assessed by the medical staff throughout the clinical trial and whenever the investigator deems necessary. As a minimum, subjects will be questioned for AEs (and concomitant therapies) at the time points indicated in the [Flow Chart](#). Assessment will be made using non-specific questions such as 'How do you feel?'. Specific questions will be asked wherever necessary in order to more precisely describe an AE.

A carefully written record of all AEs shall be kept by the investigator in charge of the trial. Records of AEs shall include data on the time of onset, end time, intensity of the event, and any treatment or action required for the event and its outcome.

The following must be collected and documented on the appropriate CRF(s) by the investigator:

- From signing the informed consent onwards until an individual subject's end of trial:
 - All AEs (serious and non-serious) and all AESIs
 - The only exception to this rule are AEs (serious and non-serious) and AESIs in Phase I trials in healthy volunteers, when subjects discontinue from the trial due to screening failures prior to administration of any trial medication. In these cases, the subjects' data must be collected at trial site but will not be entered in the CRF or trial database and will not be reported in the CTR.
- After the individual subject's end of trial:
 - The investigator does not need to actively monitor the subject for new AEs but should only report any occurrence of cancer and related SAEs and related AESIs of which the investigator may become aware of by any means of communication, e.g. phone call. Those AEs should, however, not be reported in the CRF

Proprietary confidential information © 2021 Boehringer Ingelheim International GmbH or one or more of its affiliated companies

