Trial endpoints	
Primary endpoint: Percentage of subjects with drug-related adverse events
 
Secondary endpoints:
 
Part I and II
 
Single dose part (After the first dose) ,
 
$AUC_{0-\infty}$, C_{max} and t_{max} of BI 706321
 
Part I only
 
After the last dose,
 
$AUC_{\tau,ss}$ and $C_{max,ss}$, $C_{min,ss}$, $R_{A,AUC}$, and $R_{A,Cmax}$ of BI 706321

Proprietary confidential information © 2021 Boehringer Ingelheim International GmbH or one or more of its affiliated companies

FLOW CHART

Part I:

Visit	Day	Planned time (relative to first drug administration [h:min])	Approximate clock time of actual day [h:min]	Event and comment	Safety laboratory	PK blood for BI 706321 and BI 706062 ⁸	PK urine for BI 706321 ⁹	12-lead ECG	Vital signs (BP, PR, BT)	Questioning for AEs and concomitant therapy ⁵
1	-28 to -1			Screening (SCR) ¹	x			x	x	
2	-3 to -1	-72:00 ¹¹		Admission to trial site ^{12,13}	x ¹⁴				x	x
	1	-1:00	08:00	Allocation to treatment ²		x ²	x ²	x ^{2,10}	x ²	x ²
		0:00	09:00	First drug administration			▲			
		0:30	09:30		x					
		1:00	10:00		x			x ⁷	x	
		2:00	11:00	240 mL fluid intake	x			x ⁷	x	x
		3:00	12:00		x					
		4:00	13:00	240 mL fluid intake, thereafter lunch ³	x	+		x ⁷	x	x
		5:00	14:00		x					
		6:00	15:00		x					
		8:00	17:00		x	+		x ⁷	x	x
		10:00	19:00	Dinner ³	x					
		12:00	21:00		x	+		x ⁷	x	x
	2	24:00	09:00	Breakfast ³	x	x	+	x ⁷	x	x
		36:00	20:00		x			x ⁷		x
	3	48:00	09:00		x	+		x ⁷		x
	4	72:00	09:00		x	+				
	5	96:00	09:00		x	+		x		x
	6	120:00	09:00	Drug administration ⁶	x ²	x ²	▼	x	x	x
	7	144:00	09:00	Drug administration ⁶				x	x	x
	8	168:00	09:00	Drug administration ⁶	x ²	x ²				x
	9	192:00	09:00	Drug administration ⁶		x ²		x	x	x
	10	216:00	09:00	Drug administration ⁶	x ²	x ²				
	11	240:00	09:00	Drug administration ⁶		x ²		x	x	x
	12	264:00	09:00	Drug administration	x ²	x ²	▲			x
		264:30	09:30		x					
		265:00	10:00		x					
		266:00	11:00	240 mL fluid intake	x					
		267:00	12:00		x					
		268:00	13:00	240 mL fluid intake, thereafter lunch ³	x	+				
		269:00	14:00		x					
		270:00	15:00		x					
		272:00	17:00		x	+				
		274:00	19:00	Dinner ³	x					
		276:00	21:00		x	+				
	13	288:00	09:00	Drug administration ⁶	x ²	x ²	▼	x	x	x
	14	312:00	09:00	Drug administration ⁶	x ²	x ²				x

Proprietary confidential information © 2021 Boehringer Ingelheim International GmbH or one or more of its affiliated companies

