Visit	Day	Planned time (relative to first drug administration [h:min])	Approximate clock time of actual day [h:min]	Event and comment	Safety laboratory	PK blood for BI 706321 and BI 706062 ⁸	PK urine for BI 706321 ⁹	12-lead ECG	Vital signs (BP, PR, BT)	Questioning for AEs and concomitant therapy ⁵
15	15	336:00	09:00	Drug administration ⁶		x ²			x	x
	16	360:00	09:00	Drug administration ⁶		x ²	x ²			x
	17	384:00	09:00	Drug administration ⁶		x ²		x	x	x
	18	408:00	09:00	Drug administration ⁶		x ²	x ²			x
	19	431:45	08:45			x ²		x ¹⁰	x	x
		432:00	09:00	Last drug administration			▲			
		432:30	09:30			x				
		433:00	10:00			x		x ⁷	x	
		434:00	11:00	240 mL fluid intake		x		x ⁷	x	
		435:00	12:00			x				
		436:00	13:00	240 mL fluid intake, thereafter lunch ³		x	+	x ⁷	x	
		437:00	14:00			x				
		438:00	15:00			x				
		440:00	17:00			x	+	x ⁷	x	
		442:00	19:00	Dinner ³		x				
		444:00	21:00			x	+	x ⁷	x	
		446:00	22:00			x				
20	20	456:00	09:00	Light breakfast	x	x	+	x ⁷	x	x
	21	480:00	09:00			x	+	x ⁷	x	x
	22	504:00	09:00		x	x	+	x	x	x
	23	528:00	09:00			x	+			x
	24	552:00	09:00			x	▼	x	x	x
	25	576:00	09:00			x				x
3	26	600:00	09:00			x				x
	27	624:00	09:00	End of trial (EoTrial) examination ^{4,13} / Discharge from trial site ¹²	x	x		x	x	x

1. Subject must be informed and written informed consent obtained prior to starting any screening procedures. Screening procedures include physical examination, check of vital signs, assessment of body temperature, ECG, safety laboratory (including drug screening), demographics (including determination of body height and weight, smoking status and alcohol history), relevant medical history, concomitant therapy and review of inclusion/exclusion criteria.
2. The time is approximate; the procedures are to be performed and completed within the 3 hours prior to drug administration on Day 1. On all other days the 3-hour window only applies to safety assessments and PK blood collection. Allocation to treatment may be performed at any time following enrolment but must be completed prior to (first) drug administration.
3. If several actions are indicated at the same time, the intake of fluid and meals will be the last action.
4. At the end of trial visit the EoTrial examination includes physical examination, body weight, vital signs, assessment of body temperature, ECG, safety laboratory, recording of AEs, and concomitant therapies.

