5. AEs and concomitant therapies will be recorded throughout the trial, but will be specifically asked for at the times indicated in the [Flow Chart](#) above.
6. On all non-intensive PK days, standard light breakfast will be served approx. 1 hour after the dose. On all study days standard meals (lunch and dinner) will be given approx. 4 and 10 hours post dose.
7. The ECG recording has to be performed in triplicate at this time.
8. Sampling times and periods may be adapted based on information obtained during the trial including addition of samples and visits as long as the total blood volume drawn does not exceed 400 mL per subject.

Proprietary confidential information © 2021 Boehringer Ingelheim International GmbH or one or more of its affiliated companies

9. A blank urine sample (x) is to be obtained prior to administration of trial medication. Other urine samples are to be collected over the stated post-dose intervals (◀—|—|→) 0-4, 4-8, 8-12, 12-24, 24-48, 48-72, 72-96 and 96-120 h on days 1 and 19 for all doses. For 2 mg dose group, samples over the post-dose interval 96-120 h are not to be collected (samples over the post-dose interval 0-4, 4-8, 8-12, 12-24, 24-48, 48-72, 72-96 are to be collected). On day 12, the samples are to be collected over the stated post-dose intervals (◀—|—|→) 0-4, 4-8, 8-12, 12-24 h for all dose groups.
10. At baseline (i.e. Day 1, prior to drug administration) and Day 19, 3 triplicate ECGs are recorded within approximately one hour. The recordings should be separated by at least 15 minutes.
11. This is nominal time. Actual visit procedures may be performed anytime between day -3 and day -1.
12. The hospitalization may be extended for operational reasons.
13. SARS-CoV-2/ COVID-19 test (nucleic acid amplification methods) as well as body temperature assessment will be performed once prior to admission to trial site during the period from Day -3 to Day -1, at the end of trial visit unless subject is hospitalized throughout the trial, and when the infection is suspected during the trial.
14. Safety laboratory to be taken and to be medically evaluated within 3 days prior to administration of study drug; this repeat safety laboratory can be omitted, if the screening examination is performed on Days -3, -2 or -1.

Proprietary confidential information © 2021 Boehringer Ingelheim International GmbH or one or more of its affiliated companies

Part II:

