In the SRD trial 1425-0001, one subject in the 25 mg dose group reported a brief generalized sensation of cold approximately 10 hours after dosing with associated mild transient increase in temperature (37.4°C) and CRP (35.4 mg/L [ULN: 5.0 mg/L]). In the MRD trial 1425-0002, minor transient elevations in CRP, up to a maximum value of 19.7 mg/L (ULN: 5.0 mg/L) were observed in a subset of subjects beginning after approximately 3 to 6 days of multiple dosing. CRP levels subsequently normalized within 48 to 96 hours while dosing was ongoing. Some of these subjects experienced symptoms reported as "flu like symptoms"

Proprietary confidential information © 2021 Boehringer Ingelheim International GmbH or one or more of its affiliated companies

described above, while other subjects had no such symptoms associated with these changes in CRP values. No clinically significant changes from baseline in ferritin, haptoglobin, or fibrinogen were observed. Given the minor and transient nature of these observed changes in CRP, in the absence of clinical symptoms, they were not considered clinically relevant.

In both the SRD and MRD trials there were no AEs that led to discontinuation of the study drug; neither SAE nor severe AE were observed. Vital sign evaluation and safety laboratory testing did not reveal clinically relevant findings.

No clinically relevant changes in any cardiac intervals as measured by the ECG core lab were observed in any subject exposed to BI 706321; no relevant blood pressure and heart rate changes were noted.

Trial 1425-0010, is a Phase I DDI trial to assess the effect of itraconazole on the pharmacokinetics of BI 706321 in 14 healthy male subjects using an open-label, two-period fixed sequence design. At the time of drafting of this protocol, preliminary safety data showed that 18 AEs in 10 subjects from the treated set occurred during this trial. 15 AEs in 8 subjects were assessed as drug-related; these AEs did not indicate any potential safety concern. All AEs were of mostly mild or occasionally moderate intensity; neither SAE nor severe AE were reported.

Overall, single dose administration of BI 706321 at doses of up to 25 mg and multiple-dose administration of BI 706321 at doses of up to 10 mg for up to 14 days, was generally well tolerated by the 104 healthy volunteers who have been exposed to active treatment in these studies.

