2.1.2 Primary endpoint

The primary endpoint for assessment of safety and tolerability of BI 706321 is the percentage of subjects with drug-related adverse events.

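### Part I schedules less AE questioning at steady state than after the first dose: none for 24 h after the Day 19 dose, and none on dosing Day 10

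*Protocol*

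**What the plan says.** The primary endpoint (Protocol section 2.1.2) "is the percentage of subjects with drug-related adverse events". Section 5.2.5.2.1 makes the Flow Chart the guaranteed minimum for asking about AEs: "As a minimum, subjects will be questioned for AEs (and concomitant therapies) at the time points indicated in the" Flow Chart. Footnote 5 of the Part I Flow Chart separates recording from asking. AEs are recorded throughout, "but will be specifically asked for at the times indicated in the" Flow Chart.

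The last column of that chart carries the questioning marks. Two hours after the first dose the row reads "2:00 11:00 240 mL fluid intake x x ⁷ x x": PK, triplicate ECG, vital signs and AE questioning. Two hours after the last dose it reads "434:00 11:00 240 mL fluid intake x x ⁷ x": PK, triplicate ECG and vital signs, with no AE mark. The Day 10 row reads "10 216:00 09:00 Drug administration ⁶ x ² x ²" and also ends before the AE column.

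Section 1.2.1 reports that in the earlier multiple-dose trial (1425-0002) transient CRP elevations appeared in a subset of subjects, "beginning after approximately 3 to 6 days of multiple dosing", and that some of these subjects had flu-like symptoms. Section 1.4.2.1.3 names close monitoring for AEs of infection and systemic inflammation as risk mitigation.

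**The concern.** The endpoint depends on AEs being noticed, recorded and judged drug-related. The AEs seen so far with this compound were mostly mild and short, the kind most likely to go unmentioned unless someone asks. If scheduled asking thins out once the drug has accumulated, the multiple-dose phase relies more on spontaneous report and next-day recall than the first-dose phase does.

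Two places stand out. On Day 19 the post-dose ECG and vital-sign schedule of Day 1 is repeated hour for hour, but the AE marks are not. On Day 10 CRP is drawn (Table 5.2.3: 1, column C) without a scheduled question about symptoms, and the chart marks no vital signs, hence no body temperature. Section 1.2.1 relied on the absence of symptoms when it judged the earlier CRP changes not clinically relevant, so the symptom question is what makes the Day 10 CRP value interpretable. No section explains either blank.

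**Working it through.** **Step 1: marks in the Part I AE column** (hours from first dose).
- Single-dose part: before dosing, then 2, 4, 8, 12, 24, 36, 48, 96 and 120 h.
- Multiple-dose part: 144, 168, 192, 240, 264, 288, 312, 336, 360, 384, 408 and 431:45 h.
- After the last dose (432 h): 456 h, then daily to 624 h.

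The blanks should be confirmed against the typeset chart, because some marks in the text version are shifted among the laboratory, PK and urine columns. The AE column looks reliable for these rows. The Day 8, 10 and 14 rows share one layout and differ only in the AE cell, and the Day 19 ECG times agree with SAP Table 6.7: 1.

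**Step 2: counts and gaps.**

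| Interval | AE questionings | Per 24 h |
|---|---|---|
| 0 to 24 h (first dose), counting the 24 h mark | 5, of which 4 before 24 h | 5.0 |
| 48 to 96 h (washout), counting the 96 h mark | 1 | 1/2 = 0.5 |
| 120 to 432 h (13 days) | 12 | 12/13 = 0.92 |
| 432 to 456 h (last dose), counting the 456 h mark | 1, of which 0 before 24 h | 1.0 |

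The longest gaps are 96 − 48 = 48 h (no mark on Day 4, washout), 240 − 192 = 48 h (across Day 10), and 456 − 431.75 = 24.25 h (across the Day 19 dose). Doses are given on Day 1 and Days 6 to 19, 15 in all. Day 10 alone has no AE mark.

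**Step 3: Day 10 against the CRP window.** Daily dosing starts at 120 h. The gap runs from (192 − 120)/24 = 3 days to (240 − 120)/24 = 5 days of multiple dosing, inside the reported 3 to 6 days. Section 1.2.1 gives that window for CRP. Applying it to the flu-like symptoms is an inference from their association with CRP.

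**Step 4: exposure, first dose against steady state.** The plan's own accumulation ratios (Table 1.2.1: 2; 2, 5, 8, 10 mg) are 2.00, 2.28, 3.29, 3.34 for Cmax and 2.30, 2.75, 3.69, 3.58 for AUC. Dividing the tabulated geometric means reproduces them closely:
- Cmax: 5.69/2.85 = 2.00; 14.7/6.47 = 2.27; 34.7/10.6 = 3.27; 39.9/11.5 = 3.47
- AUC: 88.1/38.3 = 2.30; 234/85.1 = 2.75; 517/140 = 3.69; 574/155 = 3.70

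The small difference at 10 mg is compatible with 7 subjects at steady state against 8 after the first dose. Median tmax at steady state was 4 to 5 h, so the Day 1 questions at 2, 4 and 8 h span the expected peak. On Day 19 no question falls there.

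**Step 5: what one subject weighs.** With 9 active subjects per dose group, one subject more or fewer with a drug-related AE moves that group's percentage by 1/9 = 11.1 points. This shows how coarse the endpoint is. It does not estimate the loss, because the documents give no rate at which unasked AEs go unreported.

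**The case against.** The case for leaving the schedule alone has real weight.

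- **The chart is only a minimum.** Section 5.2.5.2.1 also requires spontaneous reporting with onset, end time and intensity, and regular assessment by medical staff. Section 6.2.2 has AEs assessed continuously, with Part I subjects in-house to Day 27. This stands and limits the loss. It does not remove it, because only the marked times guarantee that a subject is asked.
- **The 24 h question after the last dose is asked at high exposure.** In Table 1.2.1: 2 the steady-state 24 h concentration exceeds the first-dose Cmax at every dose (3.12 against 2.85, 7.93 against 6.47, 16.4 against 10.6, 18.6 against 11.5 nmol/L). This stands, so the Day 19 gap concerns the hours around the peak, not high exposure in general.
- **Day 10 is bracketed.** Subjects are asked on Days 9 and 11, CRP is drawn on Day 10, and the earlier flu-like symptoms lasted 1 to 3 days. Many such episodes would therefore still be picked up, with a less exact onset.
- **Denser questioning after first exposure is defensible.** Section 1.4.2.1.1 names hypersensitivity as a possibility, and nothing requires Day 19 to mirror Day 1. That is fair, but it does not explain Day 10.

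A reader might infer that AEs are solicited least where exposure is highest. The chart does not support that: one of the two 48 h gaps lies in the low-exposure washout, and Day 19 keeps the roughly daily spacing of the other multiple-dose days. A reader might also infer that a low AE count on Day 19 would distort a planned result. The SAP plans no by-day AE rate. SAP section 7.8.1 counts subjects rather than events, and SAP section 6.1 uses one on-treatment phase from first dose to 16 days after the last. An event reported at 456 h therefore counts the same as one elicited at 434 h.

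**Conclusion.** The point holds as a modest weakness in data collection. Scheduled AE questioning before 24 h falls from four on Day 1 to none on Day 19, at contacts that otherwise match. Day 10 has none, which opens a 48 h gap in the period when the known CRP signal began.

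The expected effect is some loss of sensitivity for mild, transient AEs near the steady-state peak and around Day 10. Onset times would also be less precise, which matters because section 5.2.5.1.6 uses time to onset in judging causality. The effect on the endpoint percentage cannot be computed from the documents. Active and placebo subjects share one schedule, so it does not bias that comparison. It bears on informal comparison of single-dose with steady-state tolerability.

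This rests on two assumptions: that the blank AE cells are blank in the typeset chart, and that accumulation in this trial resembles that in trial 1425-0002.

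**What to change.** Add AE-questioning marks to the Part I Flow Chart at 434, 436, 440 and 444 h on Day 19, where ECG and vital signs are already taken, and at 216 h on Day 10, at the dosing contact. Apply them to all dose groups, so that the groups and the pooled placebo subjects are asked equally often.

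The cost is five short questions per in-house subject, or 5 × 48 = 240 over the planned Part I, with no new contacts. The downside is slightly more mild AEs recorded in all arms.

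If the blanks are intended, say so, give the reason, and reconcile them with the continuous assessment described in section 6.2.2. If Part I data have already been collected, state the difference in questioning frequency in the trial report wherever single-dose and multiple-dose AEs are set side by side.
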